Appendix C: INFORMED CONSENT FORM TEMPLATE

The Informed Consent Form Template will be distributed under separate cover.

Appendix D: PARTICIPATING INVESTIGATOR AND INSTITUTIONS

A list of participating Investigators and institutions will be distributed under separate cover.

Appendix E: IRB LIST

A final IRB list will be distributed under separate cover.

Appendix F: FORESEEABLE ADVERSE EVENTS

The information provided in this section pertains to foreseeable adverse events that may be observed in study subjects and may collectively assist in identifying those events for a given device or therapy that are unexpected in nature. The foreseeable adverse events information consists of two parts: a listing of potential adverse events associated with cryoablation therapy/procedure and adverse event rates reported in published literature for same therapy/procedure (see Appendix A). An evaluation of potentially anticipated events and reported events in literature may be used in combination with device labeling/IFU, current event reporting information, and other published data to assess for an unexpected occurrence.

The cryoablation procedure involves surgery, therefore, standard adverse events associated with a surgical procedure may be experienced (e.g. anesthesia complications, injury, infections, bleeding, exacerbation of pre-existing conditions, healing complications, etc.). The focus of this section is to specifically address in more detail, those events that are foreseeable due to the use, performance, and/or presence of the Arctic Front Advance™ CryoAblation Catheter under investigation.

Additional potential risks associated with the Arctic Front Advance™ CryoAblation Catheter, as well as risk minimization are discussed within section 12.

Treatment required for procedure and/or cryoablation system related adverse events that are experienced may include medication or other surgical and medical remedies. The adverse events associated with the use of the Arctic Front Advance™ CryoAblation Catheter include but are not limited to those in Table 14 and Table 15.

Table 14 pertains to the foreseeable/anticipated adverse events that may be observed in the study and may assist in identifying those adverse events that are unexpected in nature.

Table 14: Foreseeable Adverse Events

| | | |
|--------------------------|-----------------------------|------------------------|
| Anemia | Feeling cold | Pseudoaneurysm |
| Anxiety | Fever | Pulmonary edema |
| Arrhythmia | Gastrointestinal discomfort | Pulmonary embolism |
| Arteriovenous fistula | Gastroparesis | Pulmonary hemorrhage |
| Atrial fibrillation | Headache | Pulmonary hypertension |
| Atrial flutter | Heart block | Pulmonary infarction |
| Atrio-esophageal fistula | Heart failure | Pulmonary infiltration |
| Back pain | Hematemesis | Pulmonary vein |

| | | |
|--|--|--|
| | | stenosis |
| Bleeding | Hematoma | Renal impairment |
| Blurred vision | Hemoptysis | Respiratory arrest or pulmonary arrest |
| Bronchial fistula | Hemothorax | Right bundle branch block |
| Bronchitis | Hiccups | Shivering |
| Bruising | Hypertension | Shortness of breath |
| Cardiac arrest or cardiopulmonary arrest | Hypotension | Sore throat |
| Cardiac perforation or cardiac vein perforation or perforation of surrounding tissue | Hypoxia | ST segment elevation |
| Cardiac tamponade | Injury to pulmonary vein e.g. pulmonary vein dissection, pulmonary vein hematoma | Stroke or cerebrovascular accident |
| Cerebral embolism | Lightheadedness | Syncope |
| Chest discomfort or pain or pressure | Lung injury | Tachycardia |
| Coronary artery spasm | Myocardial infarction | Thrombosis or thrombus |
| Cough | Nausea | Transient ischemic attack |
| Death | Nerve injury e.g. phrenic nerve injury | Urinary infection |
| Diarrhea | Neurological impairment | Vascular access site complication |

| | | |
|---|---|-------------------------------------|
| Dizziness | Paralysis or paresis | Vasospasm |
| Dressler's syndrome | Pericardial effusion or pericardial tamponade | Vasovagal reaction |
| Dysphagia | Pericarditis | Visual changes or visual impairment |
| Embolism | Pleural effusion | Vomiting |
| Esophageal injury/damage (including atrio-esophageal fistula) | Pneumonia | |
| Fatigue | Pneumothorax or collapse of lung | |

Table 15 is a summary of reported procedure and Arctic Front Advance™ Cardiac CryoAblation Catheter related adverse events reported in a Medtronic Clinical Evaluation Report for The Arctic Front Family of Catheters Recertification (Rev 1A, 19MAY2015). The observed rate is based on the study populations that included a total of 11,242 patients.

Table 15: Arctic Front and Arctic Front Advance™ Complications Reported in Literature for Paroxysmal and Persistent AF Patients

| Events | N=11,242 Rate (95% CI*) |
|--|------------------------------------|
| Transient phrenic nerve injury (resolved prior to procedure end) | 4.26% (3.89-4.65%) |
| Phrenic nerve injury | 2.18% (1.92-2.47%) |
| Groin hematoma | 0.58% (0.45-0.74%) |
| Pericardial effusion/pericardial tamponade | 0.53% (0.41-0.69%) |
| Pseudoaneurysm | 0.36% (0.25-0.48%) |
| Hemoptysis | 0.27% (0.18-0.38%) |
| Femoral arterio-venous fistula | 0.21% (0.14-0.32%) |

| Events | N=11,242 Rate (95% CI*) |
|--------------------------------------|------------------------------------|
| Cardiac tamponade | 0.20% (0.13-0.31%) |
| Bleeding | 0.14% (0.08-0.23%) |
| Gastroparesis | 0.14% (0.08-0.23%) |
| Hematoma | 0.14% (0.08-0.23%) |
| Atrial flutter | 0.13% (0.07-0.22%) |
| Atrial tachycardia | 0.12% (0.06-0.20%) |
| Esophageal damage/ulceration | 0.12% (0.06-0.20%) |
| Transient ischemic attack | 0.12% (0.06-0.20%) |
| Stroke or cerebral vascular accident | 0.10% (0.05-0.18%) |
| Myocardial infarction | 0.05% (0.02-0.12%) |
| Atrio-esophageal fistula | 0.04% (0.01-0.10%) |
| Guidewire dissection | 0.04% (0.01-0.10%) |
| Pulmonary vein stenosis | 0.04% (0.01-0.10%) |
| ST elevation | 0.04% (0.01-0.10%) |
| Accidental femoral artery puncture | 0.03% (0.01-0.09%) |
| Inguinal aneurysm | 0.03% (0.01-0.09%) |
| Pulmonary edema | 0.03% (0.01-0.09%) |
| Difficulty swallowing/dysphagia | 0.02% (0.002-0.06%) |
| Hemothorax | 0.02% (0.002-0.06%) |
| Pericarditis | 0.02% (0.002-0.06%) |

| Events | N=11,242 Rate (95% CI*) |
|--|------------------------------------|
| Pulmonary vein hematoma | 0.02% (0.002-0.06%) |
| Thrombosis or thrombus | 0.02% (0.002-0.06%) |
| Vasovagal reaction | 0.02% (0.002-0.06%) |
| Chest discomfort or pain or pressure | 0.01% (0.0002-0.5%) |
| Cough | 0.01% (0.0002-0.5%) |
| Death | 0.01% (0.0002-0.5%) |
| Headache | 0.01% (0.0002-0.5%) |
| Hemoptysis-clinically important | 0.01% (0.0002-0.5%) |
| Inappropriate sinus tachycardia | 0.01% (0.0002-0.5%) |
| Lightheadedness | 0.01% (0.0002-0.5%) |
| Nausea | 0.01% (0.0002-0.5%) |
| Odynophagia | 0.01% (0.0002-0.5%) |
| Pneumonia | 0.01% (0.0002-0.5%) |
| Pneumothorax or collapsed lung | 0.01% (0.0002-0.5%) |
| Pulmonary infarction | 0.01% (0.0002-0.5%) |
| Pulmonary infiltration | 0.01% (0.0002-0.5%) |
| Sinus arrest/3 rd degree AV block | 0.01% (0.0002-0.5%) |
| Transient AV block | 0.01% (0.0002-0.5%) |

*95% CI calculated with binomial exact methods

Appendix G: PRE-CLINICAL TESTING

A summary of results from pre-clinical testing with the Arctic Front Advance™ Cardiac CryoAblation Catheter is provided in the Report of Prior Investigations Summary.

## 1. Version History

Version	Effective Date	Summary of Changes	Change Author
1.0	07-JUN-2017	Not Applicable, New Document	[name], Sr. Statistician  [name], Sr. Principal Statistician
2.0	09-MAY-2018	
Changes to planned analysis section (6.8) updated by removing any references about inconsistency with the CIP in the left atrial dwell time definition.
 
Changed '210 enrolled' to '210 randomized' where appropriate (section 6.3, sections 7.1 – 7.2), per the change in version 6 of the CIP on 16JAN18.
	[name], Sr. Statistician

## 2. List of Abbreviations and Definitions of Terms

Abbreviation	Definition
AAD	Anti-Arrhythmic Drug
AE	Adverse Event
AF	Atrial Fibrillation
AF/AFL/AT	Atrial Fibrillation, Atrial Flutter, or Atrial Tachycardia
Blanking period	The 90-day optimization period for the AAD arm, and the 90-day blanking period for the cryoablation arm.
CIP	Clinical Investigation Protocol
CTR	Cryo-Treated as Randomized
CTC	Cryo-Treated as Randomized 12-Month Completers
HCU	Healthcare Utilization
mITT	Modified Intention-To-Treat
PG	Performance Goal
PMA	Pre-Market Approval
QoL	Quality of Life
SAP	Statistical Analysis Plan

## 3. Introduction

---

The purpose of the Statistical Analysis Plan (SAP) for the STOP AF First trial is to provide pre-analysis documentation and rationale for the statistical procedures that will be employed in the planned analyses that are performed throughout this study. Specifically, this plan outlines methods used in the study's final report, as well as the primary study results publication. It does not limit the analysis that will be completed, as further analysis beyond what is specified in this document is likely.

This SAP was developed based on version 6.0 of the STOP AF First Clinical Investigation Protocol (referred to as the CIP in this SAP), dated 16-JAN-2018. Topics included in this document which are not included in the CIP are handling of missing data (section 6.4), subgroup analyses (section 6.7), and validation requirements (section 8).

[figure not shown]
## 4. Investigation Plan

---

The purpose of the STOP AF First study is to provide data demonstrating the safety and effectiveness of the Arctic Front Advance™ Cardiac CryoAblation Catheter for the treatment of recurrent symptomatic paroxysmal Atrial Fibrillation (AF), without the requirement that subjects be drug refractory. The current indication in the US is as follows: The Arctic Front Advance™ Cardiac CryoAblation Catheter is indicated for the treatment of *drug refractory* recurrent symptomatic paroxysmal atrial fibrillation. The proposed indication in the US is: The Arctic Front Advance™ Cardiac CryoAblation Catheter is indicated for the treatment of recurrent symptomatic paroxysmal atrial fibrillation. The proposed indication is already within the approved indications for use in Europe.

Medtronic, Inc. is sponsoring the STOP AF First study; a prospective, interventional, multi-center, randomized, controlled, unblinded clinical study. The study will compare cryoablation to Anti-Arrhythmic Drug (AAD) therapy, the current standard of care for subjects experiencing first-time repeat occurrences of paroxysmal AF. Up to 30 sites in the US, and up to 10 in Europe will participate in the trial. Two hundred and ten (210) subjects will be randomized. Subjects will be randomized 1:1 to either AAD therapy (control arm) or cryoablation (treatment arm). Subjects will be followed at 1 month, 3 months, 6 months, and 12 months following either cryoablation or AAD initiation. Subjects will be exited from the study at the 12-month follow-up visit. Guidance for procedures completed at study visits are provided in the CIP including evaluations at baseline, cryoablation procedure, and scheduled follow up visits. No interim analyses are planned.

**Figure 1: Study Design**

## **5. Study Objectives**

---

### **5.1. Primary Efficacy Objective:**

- Demonstrate the superiority of cryoballoon ablation as compared to AAD therapy in terms of the rate of freedom from AF/AT/AFL (Atrial Fibrillation, Atrial Flutter, or Atrial Tachycardia) in a non-drug refractory paroxysmal AF population.

### **5.2. Primary Safety Objective:**

- Demonstrate an acceptable safety profile of the cryoballoon ablation procedure as a first line therapy in a non-drug refractory paroxysmal AF population.

### **5.3. Secondary Objectives**

- Assess changes in Quality of Life (QoL) between baseline and 12 months in the cryoablation arm.
- Compare Health Care Utilization (HCU) between the treatment and control arms.

## 6. Statistical Methods

---

### 6.1. Study Subjects

#### 6.1.1. Disposition of Subjects

Subjects will have their eligibility assessed at baseline. The final report will provide a listing of any subjects that fail to satisfy the study's entry criteria. In the final report, a diagram or figure will describe (at a minimum) the following:

- Number of eligible subjects who consented and enrolled
- Of consented and enrolled, number randomized to cryoablation and number randomized to AAD therapy
- Subjects withdrawing consent or withdrawn by investigator prior to therapy initiation (e.g., no cryoablation despite randomization assignment due to cardiac thrombus being visible on TEE).
- Subjects with initiation of therapy as randomized.
- Withdrawals, early exits, deaths and planned study exits (i.e. after the 12-month follow-up visit) that occur after treatment initiation.

These will be described by randomized group wherever appropriate.

#### 6.1.2. Clinical Investigation Plan (CIP) Deviations

Protocol deviations will be described using frequency tables and listings. Subjects will be excluded from analysis of primary efficacy and secondary HCU objectives if the subject did not consent to the procedure/AAD therapy initiation, or if the subject withdraws consent to be studied prior to treatment.

Handling of visit window deviations as it affects the study's primary, secondary and ancillary endpoints is discussed further in section 6.2.

#### 6.1.3. Analysis Sets

The **Full analysis set** consists of all enrolled subjects who consent and meet the inclusion/exclusion criteria. [REDACTED]

The **Modified Intention-to-Treat (mITT)** cohort is the subset of subjects who maintain informed consent at least until the initiation of a cryoablation procedure or commencement of AAD treatment. For endpoints analyzed in this group of subjects, the standard intention-to-treat protocol applies immediately upon first receipt of a treatment (regardless of whether the assigned treatment was actually received). The mITT cohort will be used in the analysis of the primary efficacy objective, the secondary objectives regarding HCU and cardioversion, [REDACTED].

The **Cryo-Treated as Randomized (CTR)** set refers to eligible and consenting subjects who were randomized to cryoablation therapy and had a cryoablation procedure. The procedure is considered as

having been performed if a cryoballoon catheter was inserted into a subject's vasculature. This analytical cohort does not include AAD arm subjects who cross over into the cryoablation group, and does not include subjects who withdraw consent or are withdrawn by an investigator prior to their first day at risk for events. This set will be used in the analysis of the primary safety objective, [REDACTED].

## 6.2. General Methodology and Evaluation of Objectives

### 6.2.1. Overview

The analysis described in this SAP will be conducted by Medtronic statisticians. Prior to evaluation of the study's primary objectives, a descriptive analysis will be performed: demographic and other key baseline characteristics will be summarized by randomization group for the mITT dataset. Additional exploratory analyses of the data may be conducted as deemed appropriate.

### 6.2.2. Primary Efficacy Objective

Demonstrate the superiority of cryoballoon ablation as compared to AAD therapy in terms of the rate of freedom from AF/AT/AFL in a non-drug refractory paroxysmal AF population.

#### 6.2.2.1. Hypothesis

The hypothesis test used in assessment of the primary efficacy objective is that the proportion of subjects with treatment success at 12 months is greater in subjects using cryoballoon ablation compared to subjects using AAD therapy.

The following hypothesis will be tested in a two-sided test with  $\alpha = 0.05$ :

$$H_0: \pi_{\text{cryo}} = \pi_{\text{AAD}}$$

$$H_a: \pi_{\text{cryo}} \neq \pi_{\text{AAD}}$$

Where  $\pi_{\text{cryo}}$  and  $\pi_{\text{AAD}}$  are the proportion of treatment successes at 12 months in the modified intention-to-treat cohorts of the cryoballoon ablation and AAD groups, respectively.

#### 6.2.2.2. Endpoint Definition

A treatment success is the opposite of a treatment failure.

A subject is considered a treatment failure if he/she experiences any of the following:

- Acute procedural failure (treatment arm only), which is any of these:
  - Inability to isolate all accessible targeted pulmonary veins (assessed for entrance block and, where assessable, exit block) during the index ablation procedure, OR
  - Left atrial non-PVI ablations including but not limited to, ablation of linear lesions, OR
  - Use of a non-study device in the left atrium.
- Documented AF/AT/AFL on ambulatory monitoring/12-lead ECG after the 90-day post-ablation blanking period (treatment arm).
  - Minimum of 30 seconds on ambulatory monitoring or 10 seconds on 12-lead ECG.
  - Note: Documented occurrence and treatment of typical right-sided cavotricuspid isthmus dependent atrial flutter is not considered a failure if confirmed by entrainment maneuvers during EP testing.
- Any subsequent AF surgery or ablation in the left atrium.
- Any subsequent cardioversion after the 90-day post-ablation blanking period.
- Class I or III antiarrhythmic drug (or sotalol) use after the 90-day blanking period (treatment arm only).

The blanking period is defined as the first 90 days after the index ablation procedure (treatment arm) or AAD initiation (control arm). Recurrences of atrial arrhythmias during the blanking period will not be counted in the determination of the first clinical failure for the primary endpoint. Within the 90-day blanking period, recurrent arrhythmias can be managed with medications or cardioversions.

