5.1.4. Primary Endpoint

5.1.4.1. Primary Efficacy Endpoint

The primary endpoint is treatment success at 12 months after AAD initiation (control arm) or after the pulmonary vein isolation ablation procedure utilizing the Arctic Front Advance™ Cardiac CryoAblation Catheter (treatment arm). A treatment success is the opposite of a treatment failure.

Treatment failure is defined as any of the following components:

- a) Acute procedural failure (treatment arm only)
- b) Documented AF/AT/AFL on ambulatory monitoring/12-lead ECG after the 90 day post-ablation blanking period (treatment arm)/AAD optimization period (control arm).
 - o Minimum of 30 seconds on ambulatory monitoring or 10 seconds on 12-lead ECG.
 - o Note: Documented occurrence and treatment of typical right-sided cavotricuspid isthmus dependent atrial flutter is not considered a failure if confirmed by entrainment maneuvers during EP testing.
- c) Any subsequent AF surgery or ablation in the left atrium.
- d) Any subsequent cardioversion after the 90 day post-ablation blanking period (treatment arm)/AAD optimization period (control arm).
- e) Class I or III antiarrhythmic drug (or sotalol) use after the 90 day blanking period (treatment arm only).

The AAD optimization period is defined as the first 90 days after AAD initiation (control arm). The post-ablation blanking period is defined as the first 90 days after the index ablation procedure (treatment arm). Recurrences of atrial arrhythmias during the AAD optimization/blanking periods will not be counted in the determination of the first clinical failure for the primary endpoint.

Within the AAD optimization period/post-ablation blanking period, recurrent arrhythmias can be managed with medications or cardioversions. Reablation will be considered a primary endpoint failure at all times, including during the 90 day post-ablation blanking period.

Acute procedural failure (treatment arm only) is defined as:

- a) Inability to isolate all accessible targeted pulmonary veins (assessed for entrance block and, where assessable, exit block) during the index ablation procedure.
- b) Left atrial non-PVI ablations including but not limited to, ablation of linear lesions
- c) Use of a non-study device in the left atrium.

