15.1.2. Endpoint Definition

A treatment success is the opposite of a treatment failure.

A subject is considered a treatment failure if he/she experiences any of the following:

- Acute procedural failure (defined in section 5.1.4.1; treatment arm only)
- Documented AF/AT/AFL on ambulatory monitoring/12-lead ECG after the 90 day post-ablation blanking period (treatment arm)/AAD optimization period (control arm).
 - Minimum of 30 seconds on ambulatory monitoring or 10 seconds on 12-lead ECG.
 - Note: Documented occurrence and treatment of typical right-sided cavotricuspid isthmus dependent atrial flutter is not considered a failure if confirmed by entrainment maneuvers during EP testing.
- Any subsequent AF surgery or ablation in the left atrium.
- Any subsequent cardioversion after the 90 day post-ablation blanking period (treatment arm)/AAD optimization period (control arm).
- Class I or III antiarrhythmic drug (or sotalol) use after the 90 day blanking period (treatment arm only).

The AAD optimization period is defined as the first 90 days after AAD initiation (control arm). The blanking period is defined as the first 90 days after the index ablation procedure (treatment arm). Recurrences of atrial arrhythmias during the AAD optimization/blanking periods will not be counted in the determination of the first clinical failure for the primary endpoint. Within the 90 day AAD optimization period and 90 day post-ablation blanking period, recurrent arrhythmias can be managed with medications or cardioversions.

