### 6.2.2.4. Analysis Methods

The probability of a subject achieving success at 12 months (365 days) will be estimated using Kaplan-Meier survival analysis. The standard error will be approximated using Greenwood's formula. A two-sided 95% log-log confidence interval for the probability will be constructed. A log rank test with  $\alpha = 0.05$  will be used to assess whether the failure rate differs between treatment groups.

Day 0 is defined as either the day of the index cryoablation procedure or the day in which AAD drug therapy is initiated. For subjects with treatment failure, the survival date will be set to the date of the treatment failure. For subjects without treatment failure through 12 months, those subjects will be censored at the last study contact date recorded on a CRF, which may include the last study visit, the exit date, or death date. If a subject without a treatment failure is lost to follow-up, the censoring date will be set to the last recorded study visit date. If treatment failure occurs on the day of index treatment, survival time will be set to 0.5 days.

If an occurrence of documented AF/AT/AFL resulted from rhythm monitoring that was initiated at the 12-month visit, then the date of occurrence used in the Kaplan-Meier analysis will be the minimum of 365

days from the cryoballoon ablation procedure/date of AAD initiation, or the actual date of occurrence. This allows counting of all AF/AT/ AFL events found at the 12-month follow-up, even if the follow-up occurred after 365 days post-ablation but still within the visit window. Events found at 12-month visits outside of the window will be censored at the previous follow-up and described in deviation listings.

The survival curves from 0 to 12 months will be presented for both treatment arms.

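### SAP 6.2.2.2 omits the control-arm half of two primary-endpoint failure criteria (arrhythmia and cardioversion) and so departs from the protocol

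*SAP*

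**What the plan says.** SAP 6.2.2.2 lists five ways to fail the primary efficacy endpoint.

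- Acute procedural failure, and Class I or III drug use after blanking, are each marked as applying to the treatment arm only.
- Arrhythmia: "Documented AF/AT/AFL on ambulatory monitoring/12-lead ECG after the 90-day post-ablation blanking period (treatment arm". The parenthesis closes there and the bullet ends.
- Cardioversion: "Any subsequent cardioversion after the 90-day post-ablation blanking period". No arm is named.
- Repeat intervention: "Any subsequent AF surgery or ablation in the left atrium". No arm or time limit is given.

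The protocol states the arrhythmia component for both arms in 5.1.4.1: "Documented AF/AT/AFL on ambulatory monitoring/12-lead ECG after the 90 day post-ablation blanking period (treatment arm)/AAD optimization period (control arm". In 15.1.2 both the arrhythmia and the cardioversion components carry the two-limb window "after the 90 day post-ablation blanking period (treatment arm)/AAD optimization period (control arm". The synopsis agrees.

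Other SAP text bears on the control arm. The paragraph after the bullets says: "The blanking period is defined as the first 90 days after the index ablation procedure (treatment arm) or AAD initiation (control arm". The glossary entry for blanking period (SAP section 2) reads: "The 90-day optimization period for the AAD arm, and the 90-day blanking period for the cryoablation arm". SAP 6.2.2.4 dates an arrhythmia found at the 12-month visit by reference to "days from the cryoballoon ablation procedure/date of AAD initiation, or the actual date of occurrence". SAP 7.1 sizes the trial on 45.9% success in the AAD arm.

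**The concern.** The bullets in 6.2.2.2 are the operative rule for the primary endpoint. Two of the five are closed to controls by explicit wording. The arrhythmia and cardioversion bullets refer only to a post-ablation period, and a control treated as assigned has no index ablation. Taken literally, only left atrial ablation or AF surgery is left as a way for a control to fail.

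Two things would be at stake under that reading. First, most control-arm failures would not be counted. Second, the event times of the controls who still fail would be too late. Protocol 11.5.2 allows crossover ablation only after a control has been verified as a treatment failure, so the failure would be dated at the ablation and not at the earlier recurrence. The primary test is a log-rank test, which uses those times.

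SAP section 8 relies on independent programming to verify the primary analysis. That check is weaker when the specification supports two readings, because two programmers could each follow the SAP and obtain different event indicators.

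**Working it through.** **1. Comparison of the texts**

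| Component | Protocol 5.1.4.1 and 15.1.2 | SAP 6.2.2.2 bullet |
|---|---|---|
| Acute procedural failure | Treatment arm only | Treatment arm only |
| AF/AT/AFL | Post-ablation blanking (treatment) or AAD optimization (control) | Post-ablation blanking (treatment); nothing for control |
| Left atrial ablation or AF surgery | Both arms | Both arms |
| Cardioversion | Post-ablation blanking (treatment) or AAD optimization (control) | Post-ablation blanking; nothing for control |
| Class I or III drug use | Treatment arm only | Treatment arm only |

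The visible part of SAP 6.8 lists changes to the PV stenosis threshold and to the sample-size test. It does not list this one. Part of that section is redacted, so no more can be said.

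**2. The plan's own figure, under the both-arm endpoint**

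Inputs (SAP 7.1): success 69.9% and 45.9%, two-sided α = 0.05, power 90%, 1:1 allocation. The difference is d = 0.240 and the mean p̄ = 0.579.

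n per arm = [1.960·√(2p̄(1−p̄)) + 1.282·√(p₁q₁ + p₂q₂)]² / d²

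= [1.960 × 0.6982 + 1.282 × 0.6773]² / 0.0576 = 86.8, rounded up to 87.

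The total is 174, with power 0.9005 (SAP: 0.901). Allowing for 10% attrition, 174 / 0.9 = 193.3, or 194 for equal arms. The SAP's figures reproduce. They use 45.9%; the rounded 45% in protocol 15.1.6 would give 162.

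**3. Control success under the literal bullets**

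The planning assumption implies 100% − 45.9% = 54.1% control failures. Let c be the share of those controls who have a left atrial ablation or AF surgery within 12 months. The documents give no figure for c. Protocol 15.3.1.6 and SAP 6.2.4 say only that a large percentage of the AAD arm is expected to have a cryoballoon procedure. Assume that controls who do not fail are not ablated, in line with protocol 11.5.2. Then literal control success = 1 − 0.541c.

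| c (assumed) | Literal control success |
|---|---|
| 0 | 100% |
| 0.25 | 86.5% |
| 0.50 | 73.0% |
| 0.75 | 59.4% |
| 1 | 45.9% |

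**4. Effect on the test**

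With 87 per arm and cryo success 69.9%, let s be control success, d = 0.699 − s, SE₀ the pooled standard error and SE₁ the unpooled one.

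P(significant, favouring cryo) = Φ[(d − 1.960·SE₀)/SE₁]. For the other direction, replace d by −d.

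| Control success | Significant, favouring cryo | Significant, favouring AAD |
|---|---|---|
| 55% | 52.8% | 0.0% |
| 60% | 27.6% | 0.04% |
| 69.9% | 2.5% | 2.5% |
| 80% | 0.02% | 33.5% |
| 90% | 0.0% | 91.9% |

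This uses the chi-squared approximation that sized the trial, not the log-rank test. It shows what the literal rule would do and does not forecast the result.

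**The case against.** The strongest reply is that nobody would analyse the trial this way, and much of it stands.

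- Where 6.2.2.2 limits a component to one arm it says so with the word only. The arrhythmia bullet lacks that word, and in the protocol the same parenthesis merely labels which period belongs to which arm. It looks like the remnant of a cut phrase.
- The cardioversion bullet names no arm, and the glossary defines blanking for both arms.
- A window after AAD initiation in which recurrences are ignored makes sense only if later ones count. The dating rule in 6.2.2.4 likewise has no purpose for controls unless their arrhythmias are failures.
- The objective compares freedom from AF/AT/AFL between arms, and SAP 7.1 assumes 28 successes among 61 controls.
- SAP section 3 says the plan is based on protocol version 6.0, and protocol section 15 requires an amendment for a change to a principal feature.

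A reader might therefore infer too much in two ways. One is that the SAP deliberately restricts arrhythmia failure to the treatment arm, or reverses the meaning of control success. The text above speaks against that. The other is that the planned 24-point difference would disappear. That happens only near c = 0.301 / 0.541 = 0.56, and nothing in the documents supports that value over any other.

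What the reply does not do is supply the missing criterion. Defining a blanking period for controls, or dating their events, is not a statement that a control arrhythmia or cardioversion after that period is a failure. The reader must still infer this or go back to the protocol.

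**Conclusion.** The point holds as a textual defect in the primary-endpoint definition. Two of the five failure components in SAP 6.2.2.2 are truncated, contradict the protocol and give no control-arm criterion. It is very probably a drafting omission; the documents do not support reading it as an intended change of endpoint.

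The size is conditional. If the bullets were followed literally, control success would lie between 45.9% (all failing controls ablated) and 100% (none ablated), given the planned 54.1% failure rate and the assumptions above. The literal rule agrees with the SAP's own 45.9% only if essentially every failing control is ablated. If the programmers follow the protocol, as is likely, the omission has no numerical effect. It deserves correction because it sits in the primary endpoint.

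**What to change.** Before analysis, restore the control-arm limb in both the arrhythmia and the cardioversion bullets of SAP 6.2.2.2, so that each carries the window in protocol 15.1.2: "after the 90 day post-ablation blanking period (treatment arm)/AAD optimization period (control arm", with the parenthesis closed. Record the change in the SAP version history as an alignment with protocol 5.1.4.1 and 15.1.2.

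The cost is one phrase in each of two bullets. Because the correction restores the endpoint on which the trial was sized, 174 analysable subjects, 194 randomized for efficacy and 90.1% power all stand. No protocol amendment is needed, since the protocol text is already complete.
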